The risk to patients in this trial will be minimized by compliance with the eligibility criteria, close clinical monitoring and guidance for the investigators provided in the Investigator's Brochure. An adjudication committee will review cardiovascular events to confirm that these events have been evaluated appropriately and diagnosed correctly, while a Data Monitoring Committee (DMC) will monitor safety data from the study and the entire bimagrumab program for potential safety concerns.

As for any other investigational drug, there are unknown risks to bimagrumab, which may be serious and unforeseen.

Benefits

The benefits of bimagrumab treatment in the hip fracture population are still not known. However, it is expected that as seen in healthy volunteers and patients with sIBM, the hip fracture patients will have an increase in muscle mass that may translate to better recovery of lower extremity function and faster return to mobility. Over the course of the study, the number of falls might be reduced, which in turn reduces the risk of traumatic injuries and fractures, including secondary hip fractures.

4 Population

The study population will consist of male and female patients ≥ 60 years old, at time of randomization, who underwent surgical treatment for a low-energy fracture of the proximal femur. The study aims to screen approximately 400 patients. With an estimated screen failure rate of about 40%, approximately 245 patients, with successful surgery after hip fracture, will be randomized in more than 60 centers worldwide. Approximately 200 patients are expected to complete the 24-week treatment epoch and approximately 120 patients the full 48 -week study period.

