6.1 Information to be collected on screening failures

Patients who sign the informed consent form for the study but fail to be randomized to treatment will be considered a screening failure. IRT must be notified within 3 days and the following eCRFs pages must be completed:

- Screening Phase Disposition eCRF,
- Informed Consent eCRF,
- Demography eCRF,
- Inclusion/Exclusion eCRF,
- Adverse Events eCRF should be completed for any serious adverse events that occurred after signing the informed consent. Adverse events that are not SAEs will be followed by the investigator and collected only in the source data,
- Re-screening page (if applicable),
- Withdrawal of informed consent eCRF (if applicable),
- Death eCRF (if applicable)

Patients who were declared as screen failures that may improve with time after surgery (e.g. mobility or cognitive function) or may change at re-assessment (e.g. marginal deviation in laboratory or ECG findings), can be re-screened once, unless they are outside of the 3-42 days post-surgery window. These patients must be re-consented, and they receive a new patient number, after which all screening assessments done previously must be repeated. Therefore, given the additional burden of a re-screening, it is recommended to avoid screen failing a patient too rapidly, if the reason for screen failure is transient in nature and has a chance to improve within a short period of time.

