7.1 Adverse events

An adverse event (AE) is any untoward medical occurrence (i.e., any unfavorable and unintended sign [including abnormal laboratory findings], symptom or disease) in a patient or clinical investigation subject. Therefore, an AE may or may not be temporally or causally associated with the use of a medicinal (investigational) product.

All adverse events **occurring after informed consent is signed and until the last study visit** will be recorded on the Adverse Event CRF for all patients who enter the treatment epoch.

The occurrence of adverse events should be sought by non-directive questioning of the patient at each visit during the study. Adverse events also may be detected when they are volunteered by the patient during or between visits or through physical examination, laboratory test, or other assessments.

Abnormal laboratory values or test results constitute adverse events only if they fulfill at least one of the following criteria:

- they induce clinical signs or symptoms,
- they are considered clinically significant,
- they require therapy.

Clinically significant abnormal laboratory values or test results should be identified through a review of values outside of normal ranges/clinically notable ranges, significant changes from baseline or the previous visit, or values which are considered to be non-typical in patient with underlying disease. Investigators have the responsibility for managing the safety of individual patient and identifying adverse events. Clinically notable labs and other test abnormalities are included in [Appendix 1](#).

Adverse events should be recorded in the Adverse Events CRF under the signs, symptoms or diagnosis associated with them accompanied by the following information.

- the severity grade
 - mild: usually transient in nature and generally not interfering with normal activities
 - moderate: sufficiently discomforting to interfere with normal activities
 - severe: prevents normal activities
- its relationship to the investigational treatment (no/yes)
- its duration (start and end dates) or if the event is ongoing an outcome of not recovered/not resolved should be reported.
- whether it constitutes a serious adverse event (SAE)
- action taken regarding investigational treatment
- its outcome (not recovered/not resolved; recovered/resolved; recovering/resolving, recovered/resolved with sequelae; fatal; or unknown).

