2.7 Analysis sets

Assignment of patients to the different analysis sets detailed below will be performed prior to the unblinding of the treatment code and start of the primary analysis.

All enrolled analysis set: All enrolled patients who provided informed consent (as recorded in the Informed consent eCRF), will be deemed as the all enrolled set, as such, accounting for all enrolled patients. Patients who are re-screened and randomized will be counted only once, based on their re-screening record. Patients who are re-screened but who eventually are not randomized will also be counted once. Enrolled patients, who were not randomized (with the exception of patients re-screened and subsequently randomized) will be sorted last as part of a “Not Randomized” treatment group in by-patient data listings based on the all enrolled analysis set. Linked records will be sorted together using patient numbers and informed consent date (to order chronologically).

The following analysis sets are defined for primary and final update analysis purposes as detailed in this RAP:

Randomized analysis set: All randomized patients, regardless of whether the patient received study drug. This set will consist of all patients who provided informed consent (as recorded in the Informed consent eCRF) with a randomization number and a completed randomization date as per IRT.

Safety (SAF) analysis set: The SAF analysis set will consist of all patients who received at least one infusion of study drug. Patients will be analyzed according to the treatment actually received. If a patient received only part of the infusion (i.e. study drug infusion permanently discontinued), the patient will be regarded as having received study drug infusion and will be assigned to the SAF analysis set. At least one infusion, or part of an infusion (as recorded in the Dosage administration record – infusion eCRFs) will be used to assign patients to the SAF analysis set.

Full analysis set (FAS): The FAS will consist of all randomized patients who received at least one infusion of study drug. Patients who are randomized due to erroneous use of the IRT system and who did not receive at least one infusion of study drug will be excluded from the

FAS. Following the intent-to-treat principle, patients will be analyzed according to the treatment they were assigned to at randomization.

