2.11.1 General adverse events

Adverse events will be categorized based on date of onset or worsening relative to the first and last infusion of study drug as:

- Pre-treatment: Date of onset or worsening of the AE is prior to the start of first infusion of study drug.
- Treatment-emergent: Date of onset or worsening of the AE is on or after the start of the first infusion of study drug until the last infusion of study drug (expected per protocol at Week 20) + 56 days (see [Section 2.3](#) [Treatment pooling and data handling of pre-amendment 2] for more details).
- Post-treatment: Date of onset or worsening of the AE is after the date of last infusion of study drug (expected per protocol at Week 20) + 56 days.

Missing or incomplete AE onset dates will be imputed prior to categorization; algorithms for date imputations will be provided in RAP Module 8 (Programming Specifications). No imputation will be applied to AE end dates. Hence, if the end date is missing, the duration of the AE will be “continuing”.

All AEs reported will be listed. With the exception of the overview presentations, primarily only TEAEs/Post-treatment AEs will be summarized for each treatment group and across active bimagrumab treatment groups combined (“Active Total: Safety” - Includes bimagrumab 700 mg, bimagrumab 210 mg and bimagrumab 70 mg), overall and by region (Japan/Non-Japan) (see [Section 2.6](#) [Subgroups]). Percentages (%) will be derived relative to the number of patients “at risk” (in SAF analysis set or ongoing at the start of follow-up). At the time of the primary analysis number of patients “at risk” comprises:

- Incidence of AEs at Screening: All enrolled patients implying all patients who provided informed consent.
- Incidence of AEs in treatment: Patients assigned to the SAF analysis set regardless of study status, implying all patients entering the 24-week treatment epoch.
- Incidence of AEs in post-treatment follow-up:
 - Patients who completed treatment but are ongoing in post-treatment follow-up or who have discontinued during post-treatment follow-up.
 - Patients who prematurely discontinue treatment within the defined 24-week treatment epoch and who then continue study participation as part of the planned 4-week post-treatment follow-up.
 - Patients who completed treatment and post-treatment follow-up (study completed at the time of the primary analysis).

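### The SAP's denominator for screening adverse events includes screen failures, whose non-serious events never reach the database, so any such percentage would mix two ascertainment rules and be too low

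*SAP*

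**What the plan says.** SAP 2.11.1 lists the patients at risk for each period. For the screening period it says: "Incidence of AEs at Screening: All enrolled patients implying all patients who provided informed consent". SAP 2.7 defines that set in the same way: "All enrolled patients who provided informed consent (as recorded in the Informed consent eCRF), will be deemed as the all enrolled set". Patients who were never randomised are therefore included, and re-screened patients count once.

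The protocol's collection rules differ by patient group:

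- Screen failures, serious events (Protocol 6.1): "Adverse Events eCRF should be completed for any serious adverse events that occurred after signing the informed consent".
- Screen failures, other events (Protocol 6.1): "Adverse events that are not SAEs will be followed by the investigator and collected only in the source data".
- Treated patients (Protocol 7.1): all adverse events from consent to the last study visit "will be recorded on the Adverse Event CRF for all patients who enter the treatment epoch".

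On what will be tabulated, SAP 2.11.1 says: "With the exception of the overview presentations, primarily only TEAEs/Post-treatment AEs will be summarized for each treatment group".

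Protocol section 4 (Population) gives the planned numbers: "The study aims to screen approximately 400 patients", and "With an estimated screen failure rate of about 40%, approximately 245 patients, with successful surgery after hip fracture, will be randomized".

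**The concern.** A percentage is interpretable only if everyone in the denominator could have contributed to the numerator. Here the group is every consented patient, yet for screen failures the database holds serious events only. An all-AE or non-serious percentage on that base would combine complete capture in treated patients with SAE-only capture in the rest. No later analysis step could repair this, because the missing events exist only in site source documents.

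The rule also sits awkwardly in its own section. The sentence that introduces the at-risk groups in SAP 2.11.1 refers to the SAF or to patients ongoing at the start of follow-up, and neither contains screen failures.

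What is at stake is the correctness of any screening AE percentage produced under this line. No efficacy result and no between-arm safety comparison depends on it.

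**Working it through.** **Inputs**

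- Screened, S = 400, and randomised, R = 245 (Protocol section 4; both approximate).
- Screen failures, F = 400 − 245 = 155.
- Not in the documents, so assumed: the AE rate in screen failures relative to randomised patients, r, from 0.5 to 2; and the share of screen failures with an AE who have an SAE, s, from 0 to 0.5.
- Simplification: all 245 randomised patients enter the treatment epoch.

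**Check of the planning figures.** 400 × (1 − 0.40) = 240 against 245 stated. In reverse, 245/0.60 = 408.3, or 409 rounded up, against 400 stated. The figures agree to within about 3%. The plan states no screening AE incidence, so there is none to reproduce.

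**Step 1: non-serious events, compared with incidence among randomised patients.** Let p be the non-serious incidence in randomised patients. The numerator is 245p and the denominator 400, so the reported figure is 0.6125p, about 61% of p. This needs only the planned counts. As an illustration, an assumed p of 20% gives 49 patients: 49/400 = 12.25% as planned, against 49/245 = 20% with matched sets. The correction factor is 400/245 = 1.63.

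**Step 2: any AE, compared with true incidence among all enrolled patients.** The relative understatement is F·r·(1 − s) / (R + F·r).

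- At r = 1 this reduces to 0.3875 × (1 − s): 38.75% at s = 0, 34.9% at s = 0.1, 31.0% at s = 0.2, 27.1% at s = 0.3 and 19.4% at s = 0.5.
- At s = 0: r = 0.5 gives 77.5/322.5 = 24.0%; r = 1.5 gives 232.5/477.5 = 48.7%; r = 2 gives 310/555 = 55.9%.
- The lowest value in the assumed ranges is at r = 0.5 and s = 0.5: 38.75/322.5 = 12.0%.

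The direction is downward throughout. The size runs from 12% to 56%, depending on two quantities that the documents do not give.

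**Step 3: serious events.** SAEs after consent go on the eCRF for screen failures and treated patients alike. Numerator and denominator match, and the understatement is 0%.

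**Step 4: where such a figure could appear.** SAP 2.11.2 limits the overview tables to treatment-emergent and post-treatment events. SAP 2.11.3 does the same for the system organ class and preferred term tables. The time intervals in 2.11.1 begin at Day 1. Pre-treatment events are certain to appear only in the listings, which have no denominator.

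**The case against.** The strongest reply is that no output using this denominator is described. The exception for overview presentations in SAP 2.11.1 leads to 2.11.2, which is itself confined to treatment-emergent and post-treatment events. Whether a screening AE percentage exists at all depends on the table shells in RAP Module 7, which are not available here. This stands, and it is the main reason why the point is small. It does not make the line right: it sets a denominator for a named incidence, and a programmer who follows it would produce a wrong non-serious figure.

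A reader might also infer that the Total and Not Randomized columns would carry the error. The documents do not support that. SAP 2.5 defines Total as the four treatment groups combined, and SAP 2.5 and 2.7 use Not Randomized only to sort by-patient listings.

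Nor do the documents plan to set a screening rate against an on-treatment rate, so a spoiled background comparison cannot be claimed.

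The counts are soft. They are planning approximations, and re-screened patients receive a new number (Protocol 6.1) but count once in the all-enrolled set. If the 400 counts screening numbers, fewer than 155 screen failures enter the denominator and the ratio moves closer to 1.

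One could cite the general sentence at the end of Protocol 7.2.1, that the CRF captures serious and non-serious events. It does not displace the specific rule for screen failures, though the two should be reconciled.

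Finally, restricting to the SAF drops anyone screened out because of an adverse event. That is fair: the result is consistent ascertainment in a narrower population, and it must be labelled as such.

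**Conclusion.** The mismatch is real but minor. A non-serious screening AE percentage over all enrolled patients would be about 61% of the incidence among randomised patients. This assumes the planned counts of 400 and 245 and that all randomised patients are treated.

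It is tempting to read the planned share without non-serious capture, 155/400 = 38.75%, as a fixed understatement of about 39%. The documents do not support that. For any-AE incidence relative to all enrolled patients, it holds only if screen failures have the same AE rate as randomised patients and none of those with an AE has an SAE. Over the assumed ranges the figure is 12% to 56%.

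Screening SAE incidence is correct as planned. Arm-level columns are unaffected because screen failures belong to no arm, and all treatment-emergent comparisons are untouched. The effect is confined to any non-serious or any-AE screening percentage actually produced under this rule.

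**What to change.** In SAP 2.11.1, replace the screening line with two rules:

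- Screening AEs: use the SAF (patients who entered the treatment epoch) for both numerator and denominator, and describe the result as incidence among treated patients.
- Screening SAEs and deaths: keep all enrolled patients as the denominator, since the protocol has serious events recorded for screen failures too.

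If no screening AE percentage is intended, delete the line and leave pre-treatment events to the listings. The general CRF statement in Protocol 7.2.1 should be read as subject to the screen-failure rule in 6.1, and a short note in the SAP can say so.

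The cost is one line of SAP text and a check of the RAP Module 7 shells. No new data are needed and no other analysis changes. Any non-serious screening percentage would rise by the factor 400/245 = 1.63 at the planned counts.

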5.5.9 Discontinuation of investigational treatment or premature study discontinuation

Patients may voluntarily discontinue the investigational treatment for any reason at any time.

The investigator should discontinue investigational treatment for a given patient if, on balance, he/she believes that continuation would be detrimental to the patient's well-being.

Investigational treatment *must* be discontinued under the following circumstances:

- Use of prohibited treatment as per [Table 5-1](#).
- Any other protocol deviation that results in a significant risk to the patient's safety
- Breaking of the blind (inadvertently or for emergency reasons)
- Severe hypersensitivity reaction occurs
- Liver event definition met as per [Appendix 2](#)
- Deviations from the prescribed dose regimen for investigational treatment with 2 doses missed at any time
- Death
- Withdrawal of consent
- Sponsor decision to terminate (part of) the study

Investigational treatment *may* be discontinued under the following circumstances:

- Emergence of the adverse events that in the judgment of the investigator, taking into account the patient's overall status, prevent the patient from continuing participation in the study
- Any laboratory abnormalities that in the judgment of the investigator, taking into consideration the patient's overall status, prevents the patient from continuing participation in the study

At the time of protocol amendment #2 implementation, patients who have already received their Week 20 infusion of investigational treatment returned to the site at their next scheduled

visit and performed their End of Treatment visit. They continued as per the study visit schedule Table 6.1.

Patients who discontinue investigational treatment are NOT considered immediately withdrawn from the STUDY or to have withdrawn informed consent to participation (described in section 5.5.10). The patient must return approximately 28 days following the patient's last investigational treatment administration to complete the End of Treatment visit assessments (Table 6-1). If the patient was already off-treatment for a longer period, then the End of Treatment visit can be performed without delay. After completing the End of Treatment assessments, patients will enter a 4-week follow up and return for the End of Study visit. If the patient fails to return for these assessments for unknown reasons, every effort should be made to contact him/her as specified in Section 5.5.11.

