
* In case of investigational treatment discontinuation during the Treatment Epoch, the patient should complete the EoT Visit 4 weeks after the last investigational treatment administration. After the EoT visit is completed, the patient should return after an additional 4 weeks for an EoS visit. In case of premature study discontinuation after the Treatment Epoch, the patient should return to an EoS visit (not earlier than 4 weeks after the EoT visit)
 
Rand = randomization; BL = baseline; Folstein Mini Mental State Examination =MMSE
											

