The same convention in view of patients entering post-treatment follow-up will apply at the time of the final update analysis.

In addition to the aforementioned, all AEs will be allocated to a time interval based on the date/relative study day of onset or worsening of the AE. The denominator for each time interval will again be the number of patients who are ongoing in the study at the first day of each time interval (i.e. patients “at risk” of experiencing an AE in the given interval provided that they have entered that time interval).

The time intervals are as follows:

- Day 1 to Day 30.
- Day 31 to Day 90.
- Day 91 to Day 180.
- Day 181 to Day 270.
- Day 271 to EOS (Target Day 336).

Adverse events data will be listed by treatment group, country, patient, and by start date/relative study day of onset or worsening of the AEs such that the AEs sort chronologically within a patient. The type of AEs that will be presented are:

- General and dictionary coding.
- Deaths
- SAEs.
- Adverse events leading to discontinuation of study drug.
- Adverse events of special interest.

Duration of event (days) will be calculated for those events not indicated as ongoing:

Duration (days) = (End date of event – Start date of event) + 1 day.

The latest MedDRA dictionary version will be used for coding and will be described in a footnote.

2.11.2 Overview of treatment-emergent adverse events (TEAEs), treatment-emergent serious adverse events (TESAEs) and post-treatment adverse events

Overview of AEs (TEAEs/Post-treatment AEs) and SAEs (TESAEs/Post-treatment SAEs) will be presented for:

- AEs.
- Deaths.
- Severe AEs.
- AEs leading to discontinuation of the study drug.
- AEs suspected to be related to the study drug.
- SAEs.
- Severe SAEs.
- SAEs leading to discontinuation of the study drug.
- SAEs suspected to be related to the study drug.

The number (n) and percentage (%) of patients with at least one of the aforementioned AEs/SAEs in each overview category will be presented. If a patient reported more than one adverse event within each of the aforementioned categories the patient will be counted only once in each overview category. The number of events (E) of the aforementioned AEs/SAEs in each overview category will also be presented.

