For visit windows multiple records may exist in one particular visit window for a particular assessment (i.e. laboratory assessments). The assessment closest to the actual target visit day is chosen as the analyzable record for both continuous variables and categorical variables. If two assessments have the same distance, then the earlier one by relative study day will be chosen as the analyzable record.

Early discontinuation visit remapping

Patients who prematurely discontinue from the study for any reason, will be scheduled for an EOT visit approximately 28 days following their last study drug infusion, at which time all of the assessments listed for that visit will be performed. This visit will be realigned in the appropriate visit window using the rules described above.

After the EOT visit is completed, patients should return after an additional 4 weeks (28 days) for an EOS visit.

At the time of protocol amendment 2 implementation, patients who had already completed Week 20 were to have their EOT (Week 24) assessments performed at their next scheduled visit after which they continued the study as per protocol amendment 2.

Table 3.1 General realignment of visits (all assessment types not mentioned in Tables 3.2 to 3.7)

Study Epoch	Visit Name	Target Visit Day	Start Day of Visit Window	End Day of Visit Window
-------------	------------	------------------	---------------------------	-------------------------

Study Epoch	Visit Name	Target Visit Day	Start Day of Visit Window	End Day of Visit Window
Screening	Screening	Day -39 to -1		
Treatment	Day 1	Day 1		
	Baseline	Defined as the last available assessment (scheduled or unscheduled) prior to the start of the first infusion of study drug, including pre-dose assessments at Day 1.		
	Week 4	Day 28	2	42
	Week 8	Day 56	43	70
	Week 12	Day 84	71	98
	Week 16	Day 112	99	126
	Week 20	Day 140	127	154
	Week 24	Day 168	155	Last infusion of study drug + 56 days *
	End of Treatment (derived)	End of Treatment is defined as the last available assessment (scheduled or unscheduled) assigned to treatment and including the 56-days *.		
Post-treatment Follow-up	Week 36	252 **	Last infusion of study drug + 56 days * + 1 day	Target visit day + 42 days
	Week 48	336 **	295**	Last known date in study
	End of Study (derived)	End of Study is defined as the last available assessment (scheduled or unscheduled) assigned to the study.		

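### Post-treatment AE percentages count early treatment stoppers as at risk, although on the nominal schedule their follow-up ends at about the point where the post-treatment window opens

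*SAP*

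**What the plan says.** **Follow-up of early stoppers.** Protocol 5.5.9 says that a patient who stops treatment "must return approximately 28 days following" the last administration for the EoT visit. After that, "patients will enter a 4-week follow up and return for the End of Study visit". The footnote to Protocol Table 6-1 gives the same interval ("the patient should return after an additional 4 weeks for an EoS visit"), as does SAP 3.5.1 ("patients should return after an additional 4 weeks (28 days) for an EOS visit"). Under Protocol 7.1, AEs are recorded up to the last study visit. Under Protocol 7.2.2, SAEs reported after EoS or early discontinuation go only to the safety database, not the clinical one.

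**Numerator.** In SAP 2.11.1 an AE is post-treatment if "Date of onset or worsening of the AE is after the date of last infusion of study drug" plus 56 days. Anything earlier, from the first infusion on, is treatment-emergent.

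**Denominator.** SAP 2.4.1 and 2.11.1 list who is at risk in post-treatment follow-up. One bullet is given to patients who stop treatment within the 24-week epoch and "who then continue study participation as part of the planned 4-week post-treatment follow-up". The convention is kept for the final update analysis.

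**Time-interval AE tables.** Here SAP 2.11.1 uses a different rule: the denominator is the "number of patients who are ongoing in the study at the first day of each time interval".

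**The concern.** The numerator and denominator run on different clocks. The numerator opens at last infusion + 56 days; the denominator opens at entry to follow-up after EoT. For a stopper seen on schedule, AEs in the 4-week follow-up are classed as treatment-emergent, and the record closes at about the time a post-treatment AE could first be counted. That patient stays in the post-treatment denominator and can contribute little or nothing to the numerator.

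The same denominator serves the post-treatment AE and SAE overview, the tables by system organ class, deaths, and cardiac and orthopedic events (SAP 2.11.2 to 2.11.6). If cardiac events are frequent enough, SAP 2.11.6 also derives odds ratios and p-values from such proportions. Safety up to Week 48 is part of the stated purpose of the study (Protocol 1.2), so these tables are the main crude display of off-drug harm. The efficacy tests are not touched.

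**Working it through.** **1. Dates, in days after the last infusion.**

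| Event | Early stopper, nominal schedule | Source |
|---|---|---|
| EoT | about 28 | Protocol 5.5.9 |
| EoS, end of AE recording | about 28 + 28 = 56 | Protocol 5.5.9, Table 6-1 footnote, 7.1; SAP 3.5.1 |
| First post-treatment AE day | 57 | SAP 2.11.1 |
| Days in the post-treatment window | about 0 | 56 − 56 |

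The result does not depend on which infusion was the last. A treatment completer has the last infusion at day 140 and EoS at day 336. The window is day 197 to day 336: 336 − (140 + 56) = 140 days.

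**2. Effect on a percentage.** Let p be the post-treatment risk among patients who have time in the window, and s the share of the denominator with none. The printed figure is p × (1 − s). The relative understatement is s; the absolute shortfall is p × s.

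**3. Upper guide for s.** Protocol section 4 expects about 200 of about 245 patients to complete the treatment epoch. If all 45 others entered the 4-week follow-up, s = 45/245 = 18.4% and the factor is 200/245 = 0.82. For example, 30/200 = 15.0% would print as 30/245 = 12.2%.

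**4. Range.** The documents give neither p nor s. With p = 40% assumed:

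| s | Printed, p × (1 − s) |
|---|---|
| 5% | 38.0% |
| 15% | 34.0% |
| 18.4% | 32.6% |
| 25% | 30.0% |
| 30% | 28.0% |

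Removing patients with no time in the window returns 40% in each row.

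**5. Between arms.** With equal true risk in arms A and B, the ratio of printed percentages is (1 − s_B)/(1 − s_A). Assumed shares of 5% and 25% give 0.75/0.95 = 0.79; 10% and 20% give 0.80/0.90 = 0.89. If true risks differ, the arm with most stoppers need not lose most in absolute terms: p = 50% with s = 10% loses 5 points, while p = 20% with s = 20% loses 4.

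**6. Stoppers identified late.** Two missed doses require treatment to stop (Protocol 5.5.5, 5.5.9). If they are consecutive, the second falls about 56 days after the last infusion. Protocol 5.5.9 lets EoT follow at once for a patient already off treatment for longer, so EoS falls at about 56 + 28 = 84 days, with 84 − 56 = 28 or more days in the window. Suppose every stopper had 28 days, with constant hazard, p = 40% over 140 days and s = 25%. Each stopper's risk is 1 − 0.60^(28/140) = 9.7%, and the printed figure is 0.75 × 40% + 0.25 × 9.7% = 32.4%. That is above 30.0% but still below 40%.

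**The case against.** The best defence has four parts.

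*Stoppers are not all without time at risk.* A reader might infer that these patients could not have a post-treatment event. The documents do not support that. EoT is only approximately 28 days after the last dose, visit windows apply, and the late-identified stoppers in step 6 have about 28 or more days. This stands, and it limits the claim to stoppers on the nominal schedule.

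*Laboratory and vital sign values depend on a visit, not on accrued time.* Under SAP Tables 3.1 and 3.3 the follow-up window opens one day after last infusion + 56 days, so an EoS visit a day late supplies a post-treatment value. Newly notable values are affected only where EoS falls on or before that boundary. Laboratory shift tables need results at both Baseline and the visit, so they are not diluted in this way. This also stands.

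*Other displays are sound.* AEs in the stoppers' 4-week follow-up are not lost; they are counted as treatment-emergent over the safety set. The time-interval tables use the right risk set. Kaplan-Meier analyses, if event numbers allow them, censor at premature discontinuation. This stands as mitigation, but none of it corrects the post-treatment percentages.

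*The size is not established.* A reader might take 0.82 as a factor on every post-treatment percentage. It is not: the 45 include deaths, withdrawals of consent and losses to follow-up, and the SAP bullet counts only those who stay in the study.

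What remains is the explicit bullet, which places on-schedule stoppers in a denominator whose window they do not enter.

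**Conclusion.** The mismatch is real, and the rule as written gives understated percentages. For crude post-treatment AE, SAE, death, cardiac and orthopedic percentages, the relative understatement is at most the stoppers' share of the denominator. The only guide in the documents is an upper one of 18%. It assumes that every expected non-completer enters the 4-week follow-up and is seen on the nominal schedule; any who leave the study outright, or are identified late, make it smaller.

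A reader might go further and infer that off-drug harm will look lower on bimagrumab than on placebo. The documents give no stopping rates by arm, so neither the size nor the direction of any between-arm bias can be stated. It is a possibility that the rule leaves open.

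At the primary analysis the same rule has a second effect. Completers between Week 24 and last infusion + 56 days are also counted as at risk before their window has opened.

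**What to change.** 1. In SAP 2.4.1 and 2.11.1, and wherever being in the study when follow-up starts sets the denominator for post-treatment events, define it as patients still in the study on the day after last infusion + 56 days, whether they stopped early or completed treatment. Reword the bullet on early stoppers to match. Late-identified stoppers with follow-up beyond that day stay in; completers who have not reached it at the primary analysis drop out. This is the principle that the SAP already applies to its time-interval tables.
2. Add exposure-adjusted post-treatment rates beside the percentages. A stopper with a few days in the window would otherwise count the same as a completer with 140. SAP 2.11.6 already plans rates per 100 person-years for treatment-emergent events of special interest.
3. Reconcile the footnote to SAP Table 3.1, which gives patients who discontinued in the treatment epoch targets of EOT (derived) + 84 and + 168 days for Weeks 36 and 48, with the 4-week follow-up in Protocol 5.5.9, the Table 6-1 footnote and SAP 3.5.1.

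The cost is one definition, one derived flag, a person-time calculation and a footnote correction. No new data are needed. Post-treatment percentages will rise where patients without time in the window are removed.
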